6.2 DATA SHARING PLANS

6.2.1 Human Data Sharing Plan

What data will be shared?

I will share human data generated in this research for future research as follows:

Coded, linked data in an NIH-funded or approved public repository.

Coded, linked data in another public repository

Coded, linked data in BTRIS (automatic for activities in the Clinical Center)

Identified or coded, linked data with approved outside collaborators under appropriate agreements.

How and where will the data be shared?

Data will be shared through:

An NIH-funded or approved public repository. Insert name or names: [ClinicalTrials.gov](#), [dbGaP](#).

BTRIS (automatic for activities in the Clinical Center)

Approved outside collaborators under appropriate individual agreements.

Publication and/or public presentations.

When will the data be shared?

Before publication.

At the time of publication or shortly thereafter.

6.2.2 Genomic Data Sharing Plan

Unlinked genomic data will be deposited in public genomic databases such as dbGaP in compliance with the NIH Genomic Data Sharing Policy.

6.3 RESPONSE CRITERIA

6.3.1 Response Assessments

Tumor response will be assessed by the investigator using the Global Response Score ([41](#)) and modified severity weighted assessment tool (mSWAT) ([19](#)) for patients with MF/SS, and the International Consensus Meeting guidelines ([42](#), [43](#)) for patients with ATLL. Patient will be re-evaluated for response as outlined in the Study Calendar, Section [3.7](#).

6.3.2 Response Criteria for MF/SS

Global Response (GR) score (**APPENDIX C**) will be used for assessing response in patients with CTCL ([41](#)). GR score incorporates separate responses in each component of the TNBM staging (i.e., skin, nodes, viscera and blood; **APPENDIX C**). No patient with a global OR should have less than a PR in the skin.

Abbreviated Title: IL-15+Mogamulizumab

Version Date: 11/16/2020

The mSWAT ([19](#)) is an instrument utilized to track the skin tumor burden in MF/SS. It measures the percentage total body-surface area (TBSA, %) involvement separately for patches, plaques, and tumors within 12 body regions using the patient's palm and fingers representing 1% of TBSA. Patients with erythroderma are assessed for percentage of TBSA involved with patches and/or plaques. The percentage of TBSA for each lesion type is multiplied by a number (patch = 1, plaque = 2; tumor = 4) and summed to derive the mSWAT score. The mSWAT for each patient will be determined by the same individual at all study visits.

A complete response (CR) requires 100% clearing of skin disease and a partial response (PR) requires $\geq 50\%$ reduction in the mSWAT score compared with baseline. CR/PR requires confirmation by repeat assessment after ≥ 4 weeks. Stable disease is defined as less than 50% reduction to less than 25% increase in the mSWAT score compared with baseline. PD is defined as $\geq 25\%$ increase in the mSWAT score from baseline or $\geq 50\%$ increase in the sum of the products of the greatest diameters of pathologically positive lymph nodes compared with baseline.

Time to response is the time from the first treatment dose until the patient first meets the criteria for a 50% decrease in the GR score. The duration of response (DOR) is the time from first CR/PR until the GR score is increased from nadir to more than 50% of the difference between the baseline and nadir scores. Time to progression (TTP) is the time from start of treatment until PD. If patients goes off treatment for any purpose, this date is used for determination of TTP and/or DOR.

As “skin flares” have been described in patients with SS receiving the anti-PD-1 antibody Pembrolizumab ([44](#)), patients with SS whose only sign of PD is an increase in mSWAT score (i.e., who have normal/decreasing number of circulating Sézary cells) will continue treatment and be re-evaluated in 2-4 weeks to confirm disease progression. Patients whose PD is not confirmed on re-evaluation will be noted to have had a skin flare

Abbreviated Title: IL-15+Mogamulizumab

Version Date: 11/16/2020

Table 11: Calculating mSWAT Score

Body Region	% BSA in Body Region	Assessment of Involvement in Patient's Skin		
		Patch ¹	Plaque ²	Tumor ³
Head	7			
Neck	2			
Anterior trunk	13			
Arms	8			
Forearms	6			
Hands	5			
Posterior trunk	13			
Buttocks	5			
Thighs	19			
Legs	14			
Feet	7			
Groin	1			
Subtotal of lesion BSA				
Weighing factor		x1	x2	x4
Subtotal lesion BSA x weighing factor				

NOTE: mSWAT score equals summation of each column line.

Abbreviations: BSA, body surface area; mSWAT, modified Severity Weighted Assessment Tool.

¹ Any size lesion without induration or significant elevation above the surrounding uninvolved skin; poikiloderma may be present

² Any size lesion that is elevated or indurated; crusting, ulceration, or poikiloderma may be present.

³ Any solid or nodular lesion \geq 1cm in diameter with evidence of deep infiltration in the skin and/or vertical growth.

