6.3.4 Best Overall Response

The best overall response is the best response recorded from the start of the treatment until disease progression/recurrence (taking as reference for progressive disease the smallest measurements recorded since the treatment started).

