6.3.5 Duration of Response

The duration of response (DOR) is measured from the time measurement criteria are met for CR or PR (whichever is recorded first) until the first date that recurrent or progressive disease is objectively documented (taking as reference for progressive disease the smallest measurements recorded since the treatment started), death, or, in the absence of PD, date of last assessment.

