6.3.9 Duration of Response

Duration of overall response: The duration of overall response is measured from the time measurement criteria are met for CR or PR (whichever is first recorded) until the first date that

Abbreviated Title: IL-15+Mogamulizumab

Version Date: 11/16/2020

recurrent or progressive disease is objectively documented (taking as reference for progressive disease the smallest measurements recorded since the treatment started).

The duration of overall CR is measured from the time measurement criteria are first met for CR until the first date that progressive disease is objectively documented.

Duration of stable disease: Stable disease is measured from the start of the treatment until the criteria for progression are met, taking as reference the smallest measurements recorded since the treatment started, including the baseline measurements.

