10.4.3 Analysis of the Secondary Endpoints

The duration of response (DOR; beginning at the date clinical response is first identified), overall survival (OS), event free survival (EFS), and progression free survival (PFS) will be estimated using Kaplan-Meier curves with appropriate confidence intervals reported.

Every report of response rates and time to progression should contain all patients included in the study. For the response calculation, the report should contain at least a section with all eligible patients. Another section of the report may detail the response rate for evaluable patients only. However, a response rate analysis based on a subset of patients must explain which patients were excluded and for which reasons. 95% confidence limits will be given.

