Progressive disease	≥25% increase in skin disease from baseline or New tumors (T3) in patients with T1, T2, or T4 only skin disease or Loss of response: in those with complete or partial response, increase of skin score of greater than the sum of nadir plus 50% baseline score
Relapse	Any disease recurrence in those with complete response

Notes:

Percentages refer to mSWAT score.

A biopsy of normal appearing skin is unnecessary to assign a complete response. However, a skin biopsy should be performed of a representative area of the skin if there is any question of residual disease (persistent erythema or pigmentary change) where otherwise a complete response would exist. If histologic features are suspicious or suggestive of mycosis fungoides/Sézary syndrome, the response should be considered a partial response only.

Abbreviated Title: IL-15+Mogamulizumab

Version Date: 11/16/2020

Response in Lymph Nodes	
Response	Definition
CR	All lymph nodes are now ≤ 1.5 cm in greatest transverse (long axis) diameter by method used to assess lymph nodes at baseline or biopsy negative for lymphoma; in addition, lymph nodes that were N3 classification and ≤ 1.5 cm in their long axis and >1 cm in their short axis at baseline, must now be ≤ 1 cm in their short axis or biopsy negative for lymphoma
PR	Cumulative reduction $\geq 50\%$ of the SPD of each abnormal lymph node at baseline and no new lymph node >1.5 cm in the diameter of the long axis or >1.0 cm in the diameter of the short axis if the long axis is $1-1.5$ cm diameter
SD	Fails to attain the criteria for CR, PR, and PD
PD	$\geq 50\%$ increase in SPD from baseline of lymph nodes OR Any new node >1.5 cm in the long axis or >1 cm in the short axis if $1-1.5$ cm in the long axis that is proven to be N3 histologically OR Loss of response: $>50\%$ increase from nadir in SPD of lymph nodes in those with PR (whichever occurs first)
Relapse	Any new lymph node >1.5 cm in the long axis in those with CR proven to be N3 histologically

Abbreviations: CR, complete response; PR, partial response; SPD, sum of the maximum linear dimension (major axis) \times longest perpendicular dimension (minor axis); SD, stable disease; PD, progressive disease.

Response in Viscera	
Response	Definition

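### For MF/SS, Section 6.3.2 and Appendix C define progression differently with no stated precedence, and duration of response is defined three ways, so TTP, PFS and DOR dates depend on which text is applied

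*Combined protocol and SAP*

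**What the plan says.** **Progression in MF/SS.** Section 6.3.1 names the Global Response Score and mSWAT for MF/SS, and 6.3.2 opens by adopting the GR score of Appendix C. Section 6.3.2 then defines PD as a 25% or larger "increase in the mSWAT score from baseline", or a 50% or larger "increase in the sum of the products of the greatest diameters of pathologically positive lymph nodes compared with baseline". Its stable-disease band runs up to just under a 25% rise over baseline.

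Appendix C calls global PD when any compartment (skin, nodes, blood, viscera) has PD. For skin it keeps the 25% rule, and adds new tumors and a loss-of-response rule for patients in CR or PR: "increase of skin score of greater than the sum of nadir plus 50% baseline score". For nodes it adds a rise of more than 50% from nadir in patients with PR. Recurrence after CR is a separate Relapse category.

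**Duration of response.**
- 6.3.2 ends it when a rise from nadir passes a point set by the baseline-to-nadir difference: "until the GR score is increased from nadir to more than 50% of the difference between the baseline and nadir scores".
- 6.3.5 ends it at recurrence or progression ("taking as reference for progressive disease the smallest measurements recorded since the treatment started", wording also used in 6.3.4 and 6.3.9), and then lists "death, or, in the absence of PD, date of last assessment".
- 6.3.9 restates it ("The duration of overall response is measured from the time measurement criteria are met for CR or PR") and lists neither death nor last assessment.

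**Other dates.** In 6.3.2, TTP runs from start of treatment to PD, and a patient who stops treatment for any reason has that date used for TTP, DOR or both. PFS (6.3.6) runs from enrollment to relapse, progression or death, with no off-treatment rule. Section 10.4.3 says only that DOR, OS, EFS and PFS "will be estimated using Kaplan-Meier curves with appropriate confidence intervals reported".

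**The concern.** TTP and PFS are in the secondary objectives (1.1.2), and DOR is a listed secondary endpoint (10.1). A Kaplan-Meier curve needs one event rule and one censoring rule per endpoint. For MF/SS the text gives two PD rules and three DOR rules, and the statistical section does not choose among them. The same skin scores can give an event on one reading and a continuing observation on another.

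The trial is open-label with investigator-assessed response, and 10.2 plans 15 to 18 evaluable patients, of whom MF/SS is only a part. Section 10.4.7 then reports the secondary endpoints by diagnosis and CCR4 status. In groups that small, a few re-dated events can move a median. The results would also be hard to set beside published mogamulizumab figures if the reader cannot tell which rule was used.

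**Working it through.** The plan states no figure on this point, so there is none to reproduce. The check applies each written rule to the same scores. B is baseline mSWAT and n is the nadir.

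**Thresholds**

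| Rule | Formula | B = 80, n = 20 |
|---|---|---|
| PD, 6.3.2 | score at least 1.25 × B | 1.25 × 80 = 100 |
| PD by loss of response, Appendix C | score above n + 0.5 × B | 20 + 40 = 60 |
| End of DOR, 6.3.2 (mSWAT assumed) | score above n + 0.5 × (B − n) | 20 + 30 = 50 |

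A return to 80 is 0% over baseline. It is stable disease under 6.3.2, PD under Appendix C (80 is above 60), and past the end of response under the 6.3.2 DOR rule (80 is above 50).

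**Other nadirs, B = 100**

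| Nadir | 6.3.2 DOR ends above | Appendix C loss of response above | 6.3.2 PD from |
|---|---|---|---|
| 0 | 50 | 50 (any recurrence is Relapse) | 125 |
| 20 | 60 | 70 | 125 |
| 40 | 70 | 90 | 125 |
| 50 | 75 | 100 | 125 |

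A return to 100 is never PD under 6.3.2. Appendix C counts it for every nadir below 50. At exactly 50 it does not, because the rule requires the score to exceed 100.

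**Dates, illustrative paths.** Visits are taken every 8 weeks on treatment, then after 60, 60, 60 and 90 days (3.7, 3.6.2): weeks 8, 16, 24, 32.6, 41.1, 49.7 and 62.6, with B = 100.
- Partial response, scores 40, 20, 30, 65, 75, 100, 126. The 6.3.2 DOR ends at week 32.6, Appendix C PD falls at week 41.1, 6.3.2 PD at week 62.6, and six completed cycles end at about week 24. Response starts at week 8, so DOR is about 25, 33, 55 or 16 weeks respectively.
- Complete response at week 16, later scores 0, 10, 55, 100, 100. Appendix C Relapse falls at week 32.6, the 6.3.2 DOR ends at week 41.1, and 6.3.2 PD is not reached.

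**Which endpoint is affected.** PFS names relapse, so the second patient has a PFS event in any case. TTP runs only to PD, so under 6.3.2 that patient has no TTP event. A PR that returns to baseline counts for neither TTP nor PFS if the 6.3.2 rule is used.

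**Inputs that do not exist.** Appendix C gives the global score only as CR, PR, SD, PD or Relapse. A 50% fall in it (time to response in 6.3.2) and a baseline-to-nadir difference in it (DOR in 6.3.2) cannot be computed as written. With mSWAT substituted, a strictly literal reading of the DOR sentence, score above 0.5 × (B − n), gives 0.5 × (100 − 40) = 30 at a nadir of 40, which is below the nadir.

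**Off-treatment date.** Six cycles are 6 × 28 = 168 days, or 168 / 30.4375 = 5.5 months. Dated from the last scheduled mogamulizumab dose it is 5 × 28 + 15 = 155 days, or 5.1 months. Completing therapy is itself a removal criterion (3.9.1). Section 1.2.2.1 cites a median PFS of 7.7 months on single-agent mogamulizumab. If PFS were exponential with that median, exp(−ln 2 × 5.5 / 7.7) = 61% would be progression-free at 168 days, and 63% at 155 days. Those patients would have a TTP date set by stopping treatment while their PFS ran on. For a responder without PD, 6.3.5 uses the last assessment instead.

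**The case against.** Section 6.3.2 begins by adopting Appendix C, so its later skin and node sentences can be read as an incomplete summary, with Appendix C governing. On that reading the responder who returns from 20 to 80 has progressed. This is a fair reading, but it is not stated: 6.3.2 gives its own PD and SD limits and defines TTP as running to PD in the very next paragraph, where a reader would naturally apply the PD just defined.

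Three stronger readings are tempting, and the documents do not support them.
- A reader might infer that a full loss of response goes uncounted in this trial. That holds only if the 6.3.2 sentence is applied alone. Appendix C catches it for every nadir below half of baseline, and PFS counts relapse after CR.
- A reader might combine the 25% rule with the nadir reference in 6.3.4 and 6.3.5 to get a further threshold of 1.25 × 20 = 25. No section states a 25% rise from nadir. Those sentences are generic to both diseases, and Table 12 does use the nadir for ATLL.
- A reader might count all these thresholds against TTP and PFS. Those endpoints face two written PD rules; the 6.3.2 DOR threshold concerns DOR only.

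The reference to baseline and nadir scores suggests that mSWAT was meant where GR score is written, so that part is probably a wording slip. It still has to be corrected before the rule can be applied. It also stands that these are descriptive secondary endpoints in a small phase 1 trial, with no test or decision rule attached.

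**Conclusion.** The point holds as a conflict between two PD rules for MF/SS without stated precedence, three DOR definitions, percentage rules applied to a category, and an off-treatment date with no event or censoring status. With baseline 80 and nadir 20, the skin thresholds for progression are 100 and 60, and the 6.3.2 response ends above 50. In the illustrative PR path, the two PD rules date progression 62.6 − 41.1 = 21.5 weeks apart.

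Assumptions: mSWAT stands in for the GR score in the DOR rule; the Appendix C sum is a level the score must exceed, not the size of the rise; the paths and visit weeks are illustrative, so the gap in weeks is an example and not an expected shift; and the 61% to 63% figure rests on exponential PFS with the cited median.

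This should be corrected before analysis. MTD and toxicity endpoints are not affected.

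**What to change.** For endpoint dating only:
- Date TTP, PFS and DOR in MF/SS by Appendix C global PD or Relapse, and in ATLL by RD/PD in Table 12. State that Relapse counts for TTP.
- Remove the baseline-only PD sentence and the GR score percentage rules from the endpoint definitions in 6.3.2. Date time to response by the first global CR or PR.
- Keep 6.3.5 as the one DOR definition, with death stated as an event and other patients without PD or relapse censored at last assessment. Delete the duplicate overall-response paragraph in 6.3.9; its CR and stable-disease durations can stay.
- Delete the off-treatment sentence in 6.3.2, or state that stopping treatment without PD is not an event.
- Say how the boundary case is handled. Because Appendix C requires the sum to be exceeded, a PR with nadir exactly half of baseline that returns to baseline still does not qualify.

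Confirmed progression is also a criterion for removal from protocol therapy (3.9.1). The sponsor must reconcile the PD passages there as well; this point does not say which rule should govern treatment.

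The cost is protocol wording, with no new data. Some responders will have earlier progression dates than under the 6.3.2 rule.

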1.1.2 Secondary Objective(s)

- Determine the efficacy of combined CIV rhIL-15 and mogamulizumab treatment in patients with ATLL and MF/SS by assessing the overall response rate (ORR), time-to-progression (TTP), and progression-free survival (PFS).
- Determine the effect of CCR4 mutation status (mutated versus wild type) and presenting diagnosis (MF/SS versus ATLL, MF versus SS, acute and chronic versus lymphoma subtype ATLL) on ORR, TTP, and PFS
- Define the effects of rhIL-15 on the antibody-dependent cell-mediated cytotoxicity (ADCC) mediated by mogamulizumab, using ex-vivo peripheral blood mononuclear cells (PBMCs)

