10.4.7 Sub-Group Analyses

All secondary endpoints will be analyzed and reported separately according to the presenting diagnosis (MF/SS or ATLL, and MF, SS, acute, chronic, or lymphoma subtype ATLL) and CCR4 mutation status (mutated versus wild-type).

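### A skin-only mSWAT rise is rechecked in Sézary syndrome but not in mycosis fungoides, so the event rule differs across a comparison the plan intends to make

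*Combined protocol and SAP*

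**What the plan says.** Section 6.3.2 defines skin progression for MF and SS together, as a 25% or greater "increase in the mSWAT score from baseline". Appendix C uses the same threshold and makes progression in any one compartment global progression. Neither place asks for confirmation of progression, although 6.3.2 does require CR and PR to be confirmed.

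Section 6.3.2 then makes an exception for "patients with SS whose only sign of PD is an increase in mSWAT score", provided the number of circulating Sézary cells is normal or falling. These patients "will continue treatment and be re-evaluated in 2-4 weeks to confirm disease progression". It adds: "Patients whose PD is not confirmed on re-evaluation will be noted to have had a skin flare". The stated ground is that such flares "have been described in patients with SS receiving the anti-PD-1 antibody Pembrolizumab". MF is not mentioned, and Appendix C does not carry the exception.

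TTP (6.3.2) and PFS (6.3.6) end at progression, and best overall response (6.3.4) is counted only up to progression. Section 1.1.2 makes it a secondary objective to determine the effect of "presenting diagnosis (MF/SS versus ATLL, MF versus SS, acute and chronic versus lymphoma subtype ATLL) on ORR, TTP, and PFS". Section 10.1 lists the same comparison as an endpoint, and 10.4.7 adds: "All secondary endpoints will be analyzed and reported separately according to the presenting diagnosis".

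**The concern.** The definition of the event depends on the factor being compared. An SS patient whose only finding is a skin rise has a second chance before the rise counts; an MF patient with the same rise does not. When the two are set side by side for ORR, TTP and PFS, part of any difference may come from the rule and not from the disease. The rule can move the result in one direction only, because an SS event is either the same, later or removed. A confidence interval does not show a bias of this kind.

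Two gaps sit beside it. Sections 3.9.1 and 3.6.3 speak of *confirmed* progression for every patient but give MF no method or interval, while 3.1 and 3.5 end treatment at progression without that word. And nothing says whether a confirmed SS progression carries the date of the first rise or of the recheck.

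**Working it through.** The plan gives no figure on this point, so there is none to reproduce. The check applies its rules to one skin course under each label.

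**1. The rules side by side, for an mSWAT rise of at least 25% with no other sign of progression**

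- *Threshold:* identical in MF and SS (6.3.2, Appendix C).
- *Next step:* SS with normal or falling Sézary cells continues and is rescored in 2-4 weeks. For MF nothing is stated.
- *If the rise is not confirmed:* SS is noted as a flare, by implication not progression. In MF the first rise already meets the definition.
- *PFS, TTP, best response:* none refers to confirmation or to 3.9.1 or 3.6.3. Even if an investigator rechecked an MF patient because of the word *confirmed* in 3.9.1, the endpoint wording would still place the event at the first rise.

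**2. A worked course (invented scores, baseline mSWAT 80)**

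- Week 8: 104, (104 − 80)/80 = +30%.
- Week 11, a 3-week recheck: 72, −10%.
- Weeks 16, 20 and 24: 36, −55%.

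Labelled MF, skin only: progression at week 8, TTP about 8 weeks, best response progression, a non-responder.

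Labelled SS, with Sézary cells falling and blood in at least PR by week 16 (Appendix C needs this for a global PR when blood is involved at baseline): the week 8 rise is a flare, PR is reached at week 16 and confirmed at week 20, and the patient is progression-free at week 24 and a responder.

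The course stops at week 24 because six 28-day cycles end there (6 × 28 = 168 days) and 6.3.2 uses the off-treatment date for TTP. With one rule for both labels, the skin rise at week 8 is handled identically.

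**3. Timing for a single rise at week 8**

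Evaluations are every 8 weeks (3.7).

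- MF: event at week 8.
- SS, confirmed: week 8, or weeks 10-12 if dated to the recheck. The gap is 0 or 2-4 weeks.
- SS, not confirmed: no event from that rise. The next scheduled evaluation is week 16, so the gap is at least 8 weeks unless death or other progression intervenes.

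At 4.348 weeks per month, 2, 4 and 8 weeks are 0.46, 0.92 and 1.84 months. Divided by the 7.7-month median PFS cited for mogamulizumab in 1.2.2.1, these are 6%, 12% and 24%.

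**4. How far the overall size can be taken**

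It depends on q, the chance per evaluation of a skin-only rise that would not confirm. The documents give no value. As pure illustration, assume q is equal in both diseases and true PFS is exponential with median 7.7 months:

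- SS rule: S(24 weeks) = exp(−ln 2 × 24 / (7.7 × 4.348)) = 60.8%.
- MF rule: S × (1 − q)³ = 60.8%, 59.0%, 56.4%, 52.2% or 44.4% for q = 0, 1%, 2.5%, 5% or 10%.
- Difference: 0, 1.8, 4.5, 8.7 or 16.5 points.

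This shows direction and sensitivity. It is not an estimate.

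**5. Against sampling error**

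At most 18 evaluable patients are planned across MF, SS and ATLL (10.2). The MF group size is unknown. If it were 4, 5, 6 or 8, one reclassified patient would move a rate by 25, 20, 16.7 or 12.5 points. The 95% Agresti-Coull interval for 1 of 5 is 2% to 64%.

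**The case against.** The strongest reply is that the SS exception is not triggered by skin alone. It also needs blood evidence that the disease is not advancing, which suits a leukemic disease, and the protocol cites flares in SS and none in MF. This stands in part. The finding holds only for a skin rise without other signs of progression, and the blood condition should be kept. It does not explain why MF is left out: the cited flares arose under a different drug, and the plan gives no reason for withholding a recheck from MF.

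A second reply is that 3.9.1 and 3.6.3 already require confirmation for everyone. They govern removal from therapy and the move to survival follow-up, and they supply no MF procedure, so they soften the contrast in treatment but not in the endpoints.

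A third is that SS flares will be recorded, so the affected patients can be identified and re-dated. That is correct, and it is why a sensitivity analysis is an acceptable alternative.

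A fourth is that the groups are tiny and no MF-versus-SS test is specified. That is also correct, and it limits the severity.

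**Conclusion.** The asymmetry is real and follows from the text. For the same skin-only course, MF can have an event where SS has none or a later one, and this favours SS in the descriptive comparison of ORR, TTP and PFS. The missing dating rule adds 0 or 2-4 weeks to a confirmed SS progression. The overall size cannot be estimated from the documents, any shift lies within sampling error at these group sizes, and the MTD is not touched. The point is minor.

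Three stronger readings are tempting and not supported:

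- A reader might take the illustrative differences of up to 16.5 points as the expected bias. They rest on an unsourced rate, assumed equal in MF and SS although flares are cited only in SS, and they vanish at q = 0.
- A reader might infer that the rule would make an MF-SS difference uninterpretable, since it works in the direction of the response rates cited in 1.2.2.1 (47.1% SS, 28.6% MF). Those come from an earlier study of mogamulizumab, and recorded flares allow the SS cases here to be re-dated.
- A reader might infer that drug rash will be scored as MF progression. Section 6.3.2 calls mSWAT "an instrument utilized to track the skin tumor burden in MF/SS"; leaving rash out is at most a convention not written down, and the finding does not need it.

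**What to change.** In 6.3.2, with a note in Appendix C:

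- Apply the same 2-4 week recheck in MF and SS when an mSWAT rise is the only sign of progression, with no new tumors and no progression in nodes or viscera.
- For SS, keep the existing condition of normal or falling circulating Sézary cells; for MF, require no rise in blood involvement. Merely requiring no blood progression would be looser. A change from 3,000 to 4,800 cells/µL (+60%) is not Appendix C blood progression, because it stays below 5,000, yet the present SS rule would not let it through.
- Date confirmed progression to the first rise in both diseases, also when death, new therapy or other progression comes before the recheck. An unconfirmed rise is not progression.
- State that this is what *confirmed* means in 3.9.1 and 3.6.3 for skin-only progression.

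If the sponsor prefers to keep the recheck for SS only, report MF-versus-SS ORR, TTP and PFS a second time with the first mSWAT rise of at least 25% counted as progression in both.

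The cost is a short paragraph, a note, and one extra mSWAT per affected MF patient. Blood flow cytometry is already allowed for CTCL whatever the baseline result (3.7, footnote 15). True MF progression dates do not move. An MF patient with true skin progression could receive up to two more mogamulizumab doses and one more rhIL-15 course before a 4-week recheck. The plan already accepts continued treatment during the recheck for SS, and 3.9.1 still lets the investigator withdraw the patient.
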